### 7.3.2 Incremental Recovery of KOVALTRY

Incremental recovery will be determined by collecting a sample for KOVALTRY level before the scheduled infusion, and a second sample collected 15 to 30 min after end of the infusion.

Blood samples for KOVALTRY trough (predose) and recovery levels (15 to 30 min post infusion) will be collected in all participants at Visits 2, 4, and 5 in Part A; at Visits 2, 6, and 8 in Part B; and at additional time points based on the investigator's discretion. Infusions must be given in hospital and use the participants assigned treatment dose, rounded to full vial size.

The exact times for infusion and blood sampling before and after infusion and the dose administered will be documented in the CRF.

Infusions given at study visits will be recorded in the site participant records, which will be the source documents and will be used to enter this information in the CRF.

The samples will be collected as described in detail in the laboratory manual. All samples will be processed in the central laboratory (Part A) or local laboratory (Part B). Plasma concentrations of FVIII will be measured using a validated FVIII activity assay ("chromogenic assay" for Part A, "one-stage clotting assay" for Part B).

Samples for incremental recovery should be collected on days when the next prophylactic infusion is scheduled and at least 48 h after the last infusion prior to this. The measurements should only be performed when the participant is not actively bleeding and when FVIII:C levels are close to trough.

## 8. Safety Assessments

Planned time points for all safety assessments are provided in the SoAs (Section 1.3.1 for Part A and Section 1.3.2 for Part B).

The safety endpoints for the study include:

- FVIII inhibitor development using the Nijmegen-modified Bethesda assay. The first positive inhibitor test after a participant has started treatment with study drug will be confirmed by testing a second (separately drawn) sample in a central laboratory (Part A) or local laboratory (Part B).
- TEAEs
- Laboratory values and vital signs

The safety assessments for optional ITI treatment will be analyzed separately (see Section 9).

### 8.1 Physical Examination

- Physical examinations will be performed at Screening, Baseline, and at the Final visit/Early Termination visit.
  - A complete physical examination will include, at a minimum, assessments of the general appearance, dermatologic, head, eyes, ears, nose, mouth/throat/neck, thyroid, lymph nodes, cardiovascular, respiratory, gastrointestinal, extremities, neurological, and musculoskeletal, and review of systems.

- Investigators should pay special attention to clinical signs related to previous serious illnesses. Any abnormal finding should be documented.
- Height and weight will also be measured and recorded at the time points described in the SoAs (Section 1.3.1 for Part A and Section 1.3.2 for Part B). Body length will be measured instead of height, as age appropriate.

## 8.2 Vital Signs

- Vital signs will be measured at all visits. In case of any in-hospital infusion related AE, vital signs will be measured post-infusion for participants.
- Heart rate, body temperature, respiratory rate, and systolic and diastolic blood pressures will be assessed. Blood pressure may be deferred in infants if the appropriate size cuff or equipment is not available.
- Blood pressure and heart rate measurements should be preceded by at least 5 minutes of rest for the participant in a supine or seated position without distractions (e.g., television, cell phones).

## 8.3 Clinical Safety Laboratory Assessments

See Section 10.2 for the list of clinical laboratory tests to be performed and the SoAs (Section 1.3.1 for Part A and Section 1.3.2 for Part B) for the timing and frequency.

- The investigator must review the laboratory report, document this review, and record any clinically relevant changes occurring during the study in the AE section of the CRF. The laboratory reports must be filed with the source documents. Clinically significant abnormal laboratory findings (based on the normal reference ranges supplied in investigator training) are those that are not associated with the underlying disease, unless judged by the investigator to be more severe than expected for the participant's condition.
- All laboratory tests with values considered clinically significantly abnormal during participation in the study should be repeated until the values return to normal or baseline or are no longer considered clinically significant by the investigator.
  - If such values do not return to normal/baseline within a period of time judged reasonable by the investigator, the etiology should be identified and the Sponsor notified.
  - All protocol-required laboratory assessments, as defined in Section 1.3.1 and Section 1.3.2, must be conducted in accordance with the laboratory manual and the SoAs.
  - If laboratory values from non-protocol specified laboratory assessments performed at the institution's local laboratory require a change in participant management or are considered clinically significant by the investigator (e.g., SAE or AE or dose modification), then the results must be recorded in the CRF.

## 8.4 Adverse Events and Serious Adverse Events

As described in Section 10.3, an AE is any untoward medical occurrence in a patient or clinical study participant, associated with the use of study intervention, whether or not considered related to the study intervention. Detailed definitions and procedures for recording,

evaluating, follow-up, and reporting of all types of adverse events including SAEs can be found in Section 10.3. Events identified as adverse events of special interest (AESIs) for this study are specified in Section 8.4.7.

Any AE may be reported by the participant (or, when appropriate, by a caregiver, surrogate, or the participant's legally authorized representative or health care professional not involved in the study).

The investigator and any qualified designees are responsible for detecting, documenting, and recording events that meet the definition of an AE or SAE. They remain responsible for following up SAEs, AEs considered related to the study intervention or study procedures, or those that caused the participant to discontinue the study. Events of Special Interest have to be followed up regardless of causality or relationship to study intervention (see Section 8.4.7).

#### **8.4.1 Time Period and Frequency for Collecting AE and SAE Information**

All AEs and SAEs will be collected from the signing of the informed consent form (ICF) until the Follow-up call after the Final visit at the time points specified in the SoAs (Section 1.3.1 for Part A and Section 1.3.2 for Part B).

Medical occurrences that begin before the start of study intervention but after obtaining informed consent will be recorded on the AE Report Form of the case report form (CRF). Adverse events that in the opinion of the investigator occurred as a result of a study screening procedure will be considered non-treatment emergent adverse events and will be recorded as AEs in the eCRF.

All SAEs will be recorded and reported to the Sponsor or designee immediately and under no circumstances should this exceed 24 hours, as indicated in Section 10.3. The investigator will submit any updated SAE data to the Sponsor within 24 hours of it being available.

Investigators are not obligated to actively seek AE or SAE after conclusion of the study participation. However, if the investigator learns of any SAE, including a death, at any time after a participant has been discharged from the study, and the investigator considers the event to be reasonably related to the study intervention or study participation, the investigator must promptly notify the Sponsor.

#### **8.4.2 Method of Detecting AEs and SAEs**

The method of recording, evaluating, and assessing causality of AE and SAE and the procedures for completing and transmitting SAE reports are provided in Section 10.3.

Care will be taken to not introduce bias when detecting AEs and/or SAEs. Open-ended and non-leading verbal questioning of the participant is the preferred method to inquire about AE occurrences.

#### **8.4.3 Follow-up of AEs and SAEs**

After the initial AE/SAE report, the investigator is required to proactively follow each participant at subsequent visits/contacts. All AEs/SAEs/AESIs will be followed until resolution, stabilization, the event is otherwise explained, or the participant is lost to follow-up (as defined in Section 6.9). Further information on follow-up procedures is provided in Section 10.3.

#### **8.4.4 Regulatory Reporting Requirements for SAEs**

- Prompt notification by the investigator to the Sponsor of an SAE within 24 hours is essential so that legal obligations and ethical responsibilities towards the safety

of participants and the safety of a study intervention under clinical investigation are met.

- The Sponsor has a legal responsibility to notify both the local regulatory authority and other regulatory agencies about the safety of a study intervention under clinical investigation. The Sponsor will comply with country-specific regulatory requirements relating to safety reporting to the regulatory authority, Institutional Review Boards (IRBs)/Independent Ethics Committees (IECs), and investigators.
- Safety reports must be prepared by Sponsor for suspected unexpected serious adverse reactions (SUSAR) according to local regulatory requirements and Sponsor policy and forwarded to investigators as necessary.
- An investigator who receives an investigator safety report describing an SAE or other specific safety information (e.g., summary or listing of SAEs) from the Sponsor will review and then file it along with the Investigator's Brochure and will notify the IRB/IEC, if appropriate according to local requirements.

#### **8.4.5      Pregnancy**

Only male participants will be enrolled in this study ages <12 years and ≥12 to 65 years in Part A and <6 years in Part B. There is no target-related specific transport mechanism for KOVALTRY into semen or from semen into the conceptus. Following administration to a male participant, KOVALTRY would not be bioavailable via seminal delivery to the developing conceptus of an untreated partner. Therefore, no method of contraception is needed.

Bayer usually does not gather pregnancy information of drug exposure via father; however, if those cases are reported, details of all pregnancies in female partners of male participants will be collected after the start of study intervention and until the one-week period that is at least 5 terminal half-lives after the last dose. If a pregnancy is reported, the investigator should inform the Sponsor of learning of the pregnancy.

#### **8.4.6      Disease-Related Events and/or Disease-Related Outcomes Not Qualifying as AEs or SAEs**

The following disease related events (DREs) are common in patients with hemophilia A and can be serious/life threatening:

- Bleeding event

Any bleeding event occurring during the study will not be documented as an AE, because this is captured in the assessment of efficacy.

Because these events are typically associated with the disease under study, they will not be reported according to the standard process for expedited reporting of AEs. These events will be recorded in the EPD.

NOTE: If the bleeding fulfills the criterion for an SAE (e.g., results in hospitalization), then the event should be recorded and reported as an SAE (Section 8.4.4).

NOTE: If either of the following conditions applies, then the event must be recorded and reported as an SAE (instead of a DRE):

- *The event is, in the investigator's opinion, of greater intensity, frequency, or duration than expected for the individual participant.*

OR

- *The investigator considers that there is a reasonable possibility that the event was related to study intervention.*

#### **8.4.7 Adverse Events of Special Interest (AESI)**

The adverse events of special interest in this study are:

- Development of factor VIII inhibitors: It is mandatory that inhibitor development is assessed as “serious” and reported to the study Sponsor within 24 hours of awareness as a medical important event, following standards for SAE reporting.
- Hypersensitivity and allergic reactions including skin related and systemic reactions, such as anaphylactic reactions (seriousness should be a case by case decision).

#### **8.5 Treatment of Overdose**

Not applicable. No symptoms of overdose have been reported according to the Prescribing Information (see Section 12).

#### **8.6 Pharmacokinetics**

PK assessments will be performed in Part A only.

The PK assessments are planned in a subset of 12 children <12 years and in 12 adolescents/adults  $\geq$ 12 years. For participants <12 years old, the study would strive for balance between the two subgroups (<6y and 6 to <12y).

Based on the observed PK of KOVALTRY in prior studies, it is expected that a reduced sampling strategy will be sufficient to calculate relevant PK parameters in children below 12 years reliably.

For the PK of KOVALTRY assessment, participants will be administered a dose of 50 IU/kg. The participant must have no signs or symptoms of an acute bleeding episode. Measurement of FVIII activity of KOVALTRY will be done pre-infusion, 15 to 30 min, 4h, and 24 h post-infusion in children below 12 years and pre-infusion, 10 to 15min, 30min, 1h, 4h, 6 to 8h, 24h, and 30 to 48h in adolescent/adult participants. Samples should be collected as close as possible to the designated sampling times and at least 48 hours after previous treatment to ensure that pre-infusion KOVALTRY levels are measured at trough. If there is a delay in collecting a sample, it should still be collected. In all cases, the exact time of start and end of infusion and the time of actual sample collection should be noted in the CRF. Infusion doses for PK measurements and recovery should be given at the study center and directly reported in CRF.

The actual sampling times will be used for PK evaluation. Deviations from planned PK blood sampling times are not considered protocol deviations.

All samples will be processed in the central laboratory.

For children below 12 years, the evaluation of PK of KOVALTRY is only required once and should be performed at Visit 2.

For adolescents/adult participants 12 years or older, two PK profiles for the evaluation of PK of KOVALTRY are required. The first PK profile should be performed with start of treatment

with KOVALTRY at Visit 2. The second PK profile should be performed after approximately 6 months of treatment at Visit 5.

Based on the plasma concentration time data, the following PK parameters will be derived:  $C_{max}$ , AUC,  $AUC_{norm}$ ,  $AUC_{(0-t \text{ last})}$ ,  $AUC_{(0-t \text{ last}) \text{ norm}}$ ,  $C_{max \text{ norm}}$ , clearance, MRT,  $V_{ss}$ , and  $t_{1/2}$ .

Details about the collection, processing, storage, and shipment of samples will be provided separately (e.g., sample handling sheets or laboratory manual).

## **8.7 Pharmacodynamics**

Pharmacodynamic parameters are not evaluated in this study.

## **8.8 Genetics**

Genetics are not evaluated in this study.

## **8.9 Biomarkers**

Biomarkers are not evaluated in this study.

## **8.10 Immunogenicity Assessments**

### **8.10.1 Part A (PTPs) Immunogenicity Assessments**

All participants in Part A will be tested for Factor VIII inhibitor development at Screening, Baseline (Day 1), Visit 3, Visit 4, and Visit 5 (Month 6, End of Study/Early Termination), or in case of suspicion of Loss of Efficacy (LoE).

FVIII inhibitor testing will be done according to the Nijmegen-modified Bethesda assay. A positive inhibitor test is defined with a threshold of  $\geq 0.6$  BU at the central laboratory. If an inhibitor to the study drug (KOVALTRY) is detected after the participant has started treatment with study drug, the investigator will be notified, and repeat testing within 2 weeks of notification should be obtained. The first positive measurement will be confirmed by a second different sample. After confirmation of the positive result, the inhibitor development will be reported as SAE.

### **8.10.2 Part B (PUPs/MTPs) Immunogenicity Assessments**

In Part B, the requirement for FVIII inhibitor testing before start of study treatment at Screening and Baseline will only be done in MTPs; this assessment is not applicable for PUPs. The absence of inhibitors will be assessed by local laboratory testing at Screening ( $< 0.6$  BU/mL) of 2 consecutive samples at least 1 week but not more than 2 weeks apart.

After study treatment is started, PUPs/MTPs must be tested for development of inhibitor to study drug (KOVALTRY) at Visit 3 [approximately 5 ED], Visit 4 [approximately 10 ED], Visit 5 [approximately 15 ED], Visit 6 [approximately 20 ED], Visit 7/Interim visit [approximately 30 to 40 ED], and Visit 8/Final visit [50 ED]/Early Termination). The first positive inhibitor test must be confirmed by analysis of a second sample and by analysis of FVIII level recovery within 2 weeks of notification. After confirmation of the positive result, the inhibitor development will be reported as SAE.

## **8.11 Health Economics**

Health Economics parameters are not evaluated in this study.

## 9. Statistical Considerations

In order to reduce the risk generally associated with open-label trials, the final SAP will be available before the first participant first visit.

### 9.1 Statistical Hypotheses

The study is not designed to test any predefined hypothesis. The statistical analysis planned for the study is aimed to follow the analyses of the completed LEOPOLD studies and will be descriptive. The Statistical Analysis Plan (SAP) will provide the details of all planned analyses.

### 9.2 Sample Size Determination

#### 9.2.1 Sample Size Determination in Part A (PTPs)

The primary variable “annualized bleeding rate (ABR)” is used for the evaluation of the efficacy. The mean ABR for total bleeding episodes for previously treated severe hemophilia A study participants <12 years of age receiving prophylaxis with KOVALTRY in completed LEOPOLD Kids Part A study was  $3.75 \pm 4.98$  (median (Q1; Q3): 1.90 (0.00; 6.02)). Assuming that the average ABR for this patient population is 4 bleeding episodes and the standard deviation is 5 bleeding episodes per year, a sample size of 30 participants will allow estimating ABR by means of a 95% confidence interval with a half-width of 1.8 (the confidence interval is 2.2-5.8) which will consider to provide reasonable precision on the estimations.

For the previously treated adult/adolescent treatment arm, the proposed sample size of 12 participants is adequate for collection of PK data and will also allow for collection of supplemental efficacy and safety data in this population.

The sample size (30 children + 12 adolescents and adults) has been confirmed in consultation with China CDE as adequate to provide additional clinical data for comprehensive evaluation of efficacy, safety, and PK of KOVALTRY in Chinese hemophilia A patients.

#### 9.2.2 Sample Size Determination in Part B (PUPs/MTPs)

To fulfill the post-approval commitment enforced for KOVALTRY, the Sponsor is committed to collecting additional efficacy and safety data in previously untreated Chinese severe hemophilia A patients, in line with the CDE Technical Guideline on the Clinical Investigation of Recombinant Human Coagulation Factor VIII.

It is considered feasible to enroll approximately 6 PUPs/MTPs in Part B of this study.

Part B of this study is designed in accordance with the multinational clinical trial of KOVALTRY in previously untreated/minimally treated patients, LEOPOLD Kids Part B, where the annualized number of bleeds that occur within 48 hours after a prophylaxis infusion was the primary efficacy endpoint.

A mean of 1.9 (standard deviation 3.3) was observed for this ABR in LEOPOLD Kids Part B. Assuming the same distribution, the point estimate for the ABR within 48 hours after a prophylaxis infusion of 6 patients will be smaller than 2.9 with a probability of more than 80% (based on simulations of data for 6 patients from a negative binomial distribution).

In addition, in the SIPPET study (a multinational, prospective, randomized trial that assessed the incidence of FVIII inhibitors among PUPs treated with plasma-derived FVIII

containing von Willebrand factor or rFVIII products), the incidence of inhibitor development for the class of rFVIII products was 44.5% (95% CI: 34.7% to 54.3%).

Therefore, the true inhibitor rate for PUPs/MTPs is assumed to be within the range of 35% to 54%. With a sample size of 6 PUPs/MTPs, there is at least 92% power to observe at least 1 participant developing an inhibitor if the rate is between 35% and 54%. In case an event of inhibitor development is not observed, this sample size would provide more than 90% reassurance that the inhibitor rate should be no more than 35%.

### 9.3 Populations for Analyses

For purposes of analysis, the following populations are defined in [Table 9–1](#).

**Table 9–1: Analysis Populations**

Population	Description
Enrolled	All participants who signed the ICF or had an ICF signed on their behalf by a parent or legal representative.
Safety	Participants enrolled into the study and received at least 1 dose of study drug. The safety population will be used for the safety analysis.
Modified Intent-to-Treat (mITT)*	All study participants who have infusion/bleeding data from the EPD and/or CRF. The mITT population will be used for the efficacy analysis.
Per Protocol (PP)**	All mITT participants who completed study treatment and have at least 50 exposure days on study, without major protocol deviations.
PK analysis population	All participants with evaluable PK data will be included in the analysis of pharmacokinetic data.
ITI treatment analysis population	All participants who enter ITI treatment with study intervention will be included in the analysis for ITI treatment.

\* The ITT is inclusive of all enrolled and eligible patients. Modified ITT was introduced for this study as there is an additional condition that is to be met for participants included in ITT. This condition is that study participants need to have infusion/bleeding data from the EPD and /or CRF.

Therefore, ITT analysis population is renamed “modified ITT” for this study.

\*\* Only to be used if at least 5% of mITT participants (<12 or ≥12 years of age) are excluded from the PP population. The PP population is only in Part A; Part B will not have a PP population.

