#### Infusion of KOVALTRY

For each self-administered infusion of KOVALTRY, information must be recorded on the EPD as follows:

- a. Date and time
- b. Individual vial number (bar code scan from vial label or manual entry) and units administered
- c. Reason for treatment:
  - Prophylaxis
  - Unscheduled prophylaxis (e.g., for physical activities, suspected or non-evident bleeding following identified trauma)
  - Spontaneous bleeding first treatment
  - Trauma bleeding first treatment
  - Follow-up treatment
  - Surgery
  - ITI (only applicable to participants who develop high-titer inhibitor and received ITI)

Infusions of KOVALTRY as part of protocol mandated visits and procedures (e.g., for recovery and PK) will be recorded on the respective CRF pages.

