### Bleeding Episode

All bleeding episodes (regardless if treated or not, or treated at home or under medical supervision) as well as any potential treatment with other hemophilia drugs will be recorded in the EPD:

- a. Date and time of onset
- b. Type of bleeding (spontaneous, trauma, joint, muscle, skin/mucosal, internal, other)
- c. Location
- d. Intensity (mild, moderate, severe)
- e. Treated [yes/no]:  
If “yes”:      Date and time  
                    Product used: KOVALTRY or other  
                    Doses

If KOVALTRY is used for the treatment of a bleeding episode, the response to treatment (excellent, good, moderate, poor, too early to tell) must to be recorded. If “too early to tell” is entered, the participant will be queried for a response the next time the device is used.

For guidance to the participant or their caregiver, the following definitions for response to treatment are suggested. Individual participant responses may vary.

- **Excellent:** Abrupt pain relief and/or improvement in signs of bleeding with no additional infusion administered
- **Good:** Definite pain relief and/or improvement in signs of bleeding, but possibly requiring more than one infusion for complete resolution
- **Moderate:** Probable or slight improvement, with at least one additional infusion for complete resolution
- **Poor (or None):** No improvement or condition worsens

The following additional guidance should be used for clarification of whether information should be recorded in the EPDs or in the CRFs:

- Information on study treatment administration must be captured in either the CRFs or in the EPDs, but not both. Information should not be duplicated.
- All use of study treatment outside the hospital/clinic should be recorded in the EPD.
- Use of study treatment in the hospital/clinic as defined in the protocol (e.g., at protocol-defined visits, for PK or recovery) should be recorded in the CRFs.
  - In the extremely unlikely event that an infusion at a protocol-defined visit is given for a bleeding, the information should be recorded in the EPD rather than the CRFs, since additional information needs to be collected for bleeding that is not collected in CRFs but only in the EPD.
  - Regular prophylaxis infusions that are not defined in the protocol as being administered in the hospital/clinic at a specific visit should be recorded in the EPD regardless of whether they are administered in the hospital/clinic

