#### **9.4.2 Primary Endpoint(s)**

All efficacy analyses will be performed on the mITT population. In case of PP population (Part A only), more than 5% of participants in one arm (children or adolescents/adults) are excluded from the mITT population, and analyses for primary and secondary endpoints will be repeated in the PP population. As the non-adherence to the EPD documentation is considered independent from the treatment efficacy, the exclusion of participants without bleeding/infusion data from the EPD does not interfere with the intention-to-treat principle. These participants are excluded in order not to dilute the treatment effect.

The primary endpoint in Part A is the ABR of all bleeding episodes during prophylaxis treatment, and it will be summarized by age group (<12 y, ≥12 y) separately.

The primary endpoint in Part B is the ABR of all bleeding episodes within 48 hours of a previous prophylaxis infusion.

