### **4.5 Data Rules**

All bleed and infusion data will be entered into the electronic patient diary (hospital infusions will be entered into an eCRF) and imported into SAS. If an infusion is given for a bleed and the bleed information is not provided, the infusion date will be used as the bleed date. Bleeds occurring before start of prophylaxis treatment with study medication will not be counted.

Bleeding rate will be annualized using the following formula:

Annualized bleeding rate [per year] =

365.25 [days per year] x (# of bleeding episodes in treatment period) / duration of treatment period [in days]

The treatment period (exclude optional ITI period) is defined as from the date and time of first study treatment, until the date and time of last infusion of study medication, or last visit, whichever is later.

- “24-hour rule”: No more than 1 bleeding episode in a calendar day is counted. If there is more than 1 bleeding episode in a calendar day, to determine which bleeding episodes are counted, priority is given to treated bleeding episodes, spontaneous or trauma bleeding episodes, then joint bleeding episodes. Otherwise, the first bleeding episode in the day is counted. Severity and treatment response will be the worst value of the bleeding episodes of the day. The bleeding site will be aggregated over all bleeding events from that day. Regardless of which bleed is selected, the time of the first bleed in the day will be used. All other infusions in the day for treating bleeds will be considered follow-up infusions.
- “72-hour rule”: A spontaneous joint or spontaneous muscle bleeding episode will not be counted if it occurs within 72 hours of a prior bleeding episode (or infusion for that bleeding episode) at the same site. For a bleeding episode to be affected by this rule, all sites listed for the bleeding episode must be the same sites specified in the previous bleeding episode. If the current and previous bleeds are both skin/mucosa bleeds, this rule does not apply. Infusions for such bleeding episodes will be considered to be follow-up infusions.

See example below how these bleeds will be counted.

- Subject 1 reported => in analysis data set

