#### Modified Intent-To-Treat (mITT)

All study participants who have infusion/bleeding data from the EPD and/or CRF will be included in mITT. The mITT population will be used for the efficacy analysis.

The ITT is inclusive of all enrolled and eligible patients. Modified ITT was introduced for this study as there is an additional condition that is to be met for participants included in ITT. This

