### 6.2 Efficacy

All efficacy analyses will be performed on the mITT population. In case more than 5% of participants in one arm (children or adolescents/adults) are excluded from the mITT population, the analyses for primary and secondary endpoints will be repeated in the PP population.

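### The mITT definition lets a treated participant with no diary data into the primary ABR at zero bleeds, although Protocol 9.4.2 says such participants are excluded

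*Protocol*

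**What the plan says.** **Set definition.** Protocol Table 9–1 takes into mITT "All study participants who have infusion/bleeding data from the EPD and/or CRF". SAP 5.1 repeats it: "All study participants who have infusion/bleeding data from the EPD and/or CRF will be included in mITT". A CRF infusion record alone is enough.

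**Exclusion statement.** Protocol 9.4.2 argues that "the exclusion of participants without bleeding/infusion data from the EPD does not interfere with the intention-to-treat principle", and adds: "These participants are excluded in order not to dilute the treatment effect".

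**Where data are recorded.** Protocol 7.3.1 states: "Infusions of KOVALTRY as part of protocol mandated visits and procedures (e.g., for recovery and PK) will be recorded on the respective CRF pages". The same section sends bleeds to the EPD: "All bleeding episodes (regardless if treated or not, or treated at home or under medical supervision". It adds that the bleed details are collected in the EPD and not in the CRF.

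**ABR.** Protocol 9.4.1 and SAP 4.5 divide counted bleeds by the whole treatment period, which runs "until the date and time of last infusion of study medication, or last visit, whichever is later". SAP 4.2 gives every subject an ABR, dropouts included. SAP 4.3 has imputation rules for AE and medication dates and rules out any other imputation. Neither document has a rule for missing diary data.

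**Per-protocol trigger.** SAP 6.2 repeats the analyses in the PP set "In case more than 5% of participants in one arm (children or adolescents/adults) are excluded from the mITT population". Protocol 9.4.2 has similar wording. Table 9–1 and SAP 5.1 instead use the PP set when 5% or more of the mITT participants in an age group fall outside it.

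**The concern.** The two statements about who is analysed cannot both be followed. Under the definition, a treated participant who never used the diary is analysed. Under Protocol 9.4.2, that participant is left out.

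The choice affects the estimate in one direction only. Without a diary there are essentially no recorded bleeds, but the treatment period still counts as follow-up. The participant adds time and no events, so the mean ABR falls. The study is single-arm and open-label, and Protocol 9.4.1 plans a numerical comparison with the completed LEOPOLD trials. A lower ABR therefore reads as better efficacy.

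The usual backstop is a per-protocol repeat. Its trigger is worded in two ways, and Part B has no PP set.

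**Working it through.** **1. The plan's own figure.** Protocol 9.2.1 gives n=30 children, mean ABR 4, SD 5 and a half-width of 1.8. Check: 1.96 × 5/√30 = 1.79, interval 2.2 to 5.8. This agrees (the t quantile would give 1.87).

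**2. Who qualifies without a diary.** The first Part A dose is given at the study center (Protocol 7.1.2). Recovery infusions are given in hospital and documented in the CRF at Visits 2, 4 and 5 in Part A and Visits 2, 6 and 8 in Part B (Protocol 7.3.2). Every treated Part A participant should therefore have a CRF infusion record, so the data condition removes almost nobody. Part B participants reach the same position with their first recovery infusion.

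**3. What the formula returns.** With no recorded bleeds over D days: 365.25 × 0 / D = 0.

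**4. Shift in the mean.** Let k of N participants have no diary, and let them truly bleed at the group mean m. The reported mean is m × (N − k)/N. The reported variance is ((N − k)/N) × (SD² + m²) − (reported mean)². The values of k are assumptions. For Part A children (N=30, m=4, SD=5):

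| k | Reported mean | Change | Half-width as written | Half-width if the k are excluded |
|---|---|---|---|---|
| 0 | 4.00 | 0 | 1.79 | 1.79 |
| 1 | 3.87 | −3.3% | 1.78 | 1.82 |
| 3 | 3.60 | −10% | 1.75 | 1.89 |
| 6 | 3.20 | −20% | 1.70 | 2.00 |

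The last column is 1.96 × 5/√(30 − k), and the mean there stays at 4.0. As written, the biased estimate also looks more precise.

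For one participant in the smaller groups:
- Adolescents/adults: 1/12 = 8.3%.
- Part B: 1/6 = 16.7%. With the mean of 1.9 from Protocol 9.2.2, 1.9 × 5/6 = 1.58.

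**5. Per-protocol trigger.** A Part A participant known only from a few CRF visit infusions cannot show 50 exposure days and so falls outside PP. Under Table 9–1 and SAP 5.1:
- 1 of 30 children = 3.3%, not triggered.
- 2 of 30 children = 6.7%, triggered.
- 1 of 12 adolescents/adults = 8.3%, triggered.

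Under the SAP 6.2 wording, the same participants are inside mITT and count for nothing. The other difference, at least versus more than 5%, has no effect at the planned sizes: 5% of 30 is 1.5 and 5% of 12 is 0.6, neither a whole number.

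**6. Partial diaries, kept apart.** With diary coverage f in k participants, the reported mean is m × (1 − (k/N)(1 − f)). Six of 30 at half coverage gives 4 × (1 − 0.2 × 0.5) = 3.6. These participants have EPD data and enter mITT under either wording.

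**The case against.** **The operative rule is clear.** The same definition stands in Table 9–1, its footnote and SAP 5.1. Only one explanatory passage, in Protocol 9.4.2, differs, and SAP 6.2 does not repeat it. This is fair as a reading of precedence. But that passage states what the set is meant to achieve, and the definition does not achieve it.

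**Zero is an inference.** No text says that a missing diary counts as no bleeds. SAP 1 places data-handling details in a separate Analysis Datasets document, which is not available here, and SAP 5.1 leaves set assignment to the data review. This stands: the result follows from the formula and the absence of a rule.

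**Safeguards.** Investigators verify diary data, staff call about every two weeks, and Protocol 6.8.3 requires withdrawal when poor EPD entry compromises critical data. SAP 4.5 derives a bleed from an infusion given for one, and bleeds meeting SAE criteria are also reported as SAEs. These should keep numbers low. The derived bleed helps little here, because bleed-treatment infusions belong mainly in the EPD. Withdrawal does not remove anyone from mITT.

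**Size.** One child in 30 shifts the mean by 0.13 against a half-width of 1.8. No hypothesis is tested, and medians and quartiles are also reported. In the paediatric reference study in the package insert 45.1% had no bleeds, so a zero would often be correct for an individual. All true. The percentages above are expected shifts, and they matter most in the two small groups.

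**Stronger readings the documents do not support.** A reader might infer that the CRF wording also lets partial diaries in; they enter either way, and Protocol 9.4.2 does not mention them. A reader might also infer from SAP 6.2 that the PP analysis would rarely run; SAP 5.1 and Table 9–1 already state a workable trigger.

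**Conclusion.** The point holds for participants with no diary data. As written, they enter mITT through CRF visit infusions and receive an ABR of 0, contrary to the exclusion described in Protocol 9.4.2. The bias is downward, which is favourable to the product.

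Illustratively, one such participant lowers the group mean by 3.3% (children), 8.3% (adolescents/adults) or 16.7% (Part B). This assumes that he would have bled at the group mean and that no unseen specification sets his ABR to missing. The number of such participants is not in the documents and may be zero.

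The trigger in SAP 6.2 is a wording inconsistency to correct. It does not show that the PP analysis is lost.

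Undocumented time in partial diaries is a genuine but separate gap, of unknown size.

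**What to change.** 1. Define the mITT set for the ABR analyses as dosed participants with infusion or bleeding data in the EPD, deleting the CRF alternative in Table 9–1 and SAP 5.1. A participant with diary infusions and no bleeds stays in, so true zeros are kept.
2. Report the present EPD-or-CRF set as a sensitivity analysis.
3. Word the trigger in SAP 6.2, and the matching sentence in Protocol 9.4.2, as in Table 9–1 and SAP 5.1.
4. Separately, add a sensitivity analysis for partial diaries that removes prolonged gaps from the denominator, for example runs of planned prophylaxis infusions with no EPD record. The compliance calculation in SAP 6.1.2 already needs these data.

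Do not limit the primary denominator to days with diary entries. The diary records infusions and bleeds only, and no databased confirmation of bleed-free time from the calls is described. Such a rule could discard genuine bleed-free time and inflate the ABR.

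**Cost.** Wording changes and one derived variable for the gap analysis. The analysed n may fall slightly, with a half-width of 1.82 instead of 1.79 if one of 30 children is excluded, and the reported ABR may be slightly higher.
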